IEC	Independent Ethics Committee
IMP	Investigational Medical Product
IOP	Intraocular pressure
IRB	Institutional Review Board
ITT	Intent-to-Treat
logMAR	Logarithmic Minimum Angle of Resolution
MedDRA	Medical Dictionary for Regulatory Activities
NSAID	Non-steroidal anti-inflammatory drug
OD	Oculus dexter (Right eye)
OTC	Over the Counter
OS	Oculus sinister (Left eye)
PP	Per protocol
PPE	Personal protective equipment
PT	Preferred Term
SAE	Serious adverse event
SAP	Statistical Analysis Plan
SOC	System/Order/Class
SOP	Standard Operating Procedures
TEAE	Treatment emergent adverse event
UPT	Urine Pregnancy Test
US	United States
VA	Visual acuity

Summary

Study Number	AG-920-CS303	
Clinical Phase:	Phase 3	
Type of study	Safety	
Name of Investigational product:	Articaine Sterile Topical Ophthalmic Solution (AG-920)	
Duration of treatment per subject	1 day	
Objectives and Endpoints:	Primary Objective To evaluate the ocular safety of a single topical ocular administration of Articaine Sterile Topical Ophthalmic Solution (2 drops 30 seconds apart)	Primary Endpoints Visual acuity, intraocular pressure, biomicroscopy, AEs, TEAEs, SAEs, withdrawals due to TEAEs
	Secondary Objectives A subset of up to 20 subjects (with expectations that 12 receiving AG-920 and 6 receiving vehicle) will undergo specular microscopy prior to and 3 months after receiving masked study medication to evaluate the effect of AG-920 on corneal endothelial cell count (ECC).	Secondary Endpoints Mean change from baseline in corneal endothelial cell density after treatment with AG-920
Subject Population:	Healthy volunteers Exclusion criteria may be found in Section 4.2.	
Design:	Randomized, placebo (vehicle) controlled, double-masked, parallel-group. Unequal randomization (2:1 Active:Placebo)	
Visit Schedule:	Study visits will consist of: 
 • a 1-3 day Screening Period • a dosing visit (multiple timepoints over 90 minutes) • a follow-up phone call 1-4 days following dosing And 
 • a follow-up visit at 90-95 days following dosing (ONLY for the subset of subjects participating in the ECC evaluation) 	
Number of Investigational Sites:	Up to 5 US sites	
Estimated Total Sample Size:	240 total evaluable subjects; 160 AG-920; 80 Placebo.	

	A subset of up to 20 of subjects will have specular microscopy performed.

1 INTRODUCTION

American Genomics is evaluating the formulation of articaine, an approved local anesthetic, for topical ocular use to provide local anesthesia for intravitreal injections. The Sponsor intends to develop Articaine Sterile Topical Ophthalmic Solution (AG-920) for topical ocular use to induce local anesthesia for intravitreal injection.

Injections of pharmacologic agents into the vitreous cavity for the purpose of treating various disorders of the retina as well as intraocular inflammatory disease have become the mainstream. In almost all cases, these injections are made through the pars plana. An injection into the eye in this location, with the needle oriented properly, will be posterior to the human lens or an intraocular implant, but anterior to the retina, thereby avoiding damage to these important structures. The pars plana is a zone that rings the eye extending from 3.0 mm to 5.5 mm from the edge of the cornea (Figure 1).

Figure 1: Human Ocular Structure (coronal view)

While topical agents such as proparacaine achieve excellent anesthesia on the external surface of the eye, they do not numb the internal aspect of the pars plana, which is extremely sensitive. Currently, physicians fall into one of two methodologies: either injecting lidocaine under the conjunctiva first and then executing a second injection through the pars plana, or by using topical lidocaine gel and then performing the intravitreal injection. Patients often report moderate to severe discomfort with each of these approaches. The purpose of the AG-920 topical drop would be to allow a technician to apply the topical solution to the eye, allow the articaine to penetrate the pars plana sufficiently to permit the intravitreal injection without undue discomfort. Articaine was selected for this procedure based upon its clinical use in dental procedures, which suggest it penetrates soft tissue and bone.

1.1 Findings from nonclinical and clinical studies

1.2 Potential Risks and benefits to human subjects

Minimal risks are expected with AG-920. Based upon clinical trials conducted to date, expected risks for subjects may include temporary, mild conjunctival/ocular hyperemia, eye pain, instillation site reaction (stinging/burning), and conjunctival hemorrhage. upon instillation of the investigational medicinal product (IMP). For any additional information on AG-920 use, please refer to the [Investigator's Brochure](#).

As this study is to be conducted in healthy subjects, there is no anticipated benefit other than the possibility that a subject's participation in the present study may help others in the future to have more options for local anesthesia before ophthalmic procedures.

Any new, unexpected adverse events (AEs) present among subjects in this clinical trial will be communicated to Investigators and to ethics committees or Institutional Review Board (IRBs) in accordance with local regulations.

1.3 Design justification

Route of administration, dosage, dosage regimen, and treatment period(s)

[REDACTED]

[REDACTED]

The intended route of administration for AG-920 is topical ocular in this study. Each dose will consist of two drops 30 seconds apart in the study eye. This study consists of a single treatment and subjects will be randomized 2:1 to AG-920 or Placebo.

2 OBJECTIVES AND ENDPOINTS

Primary Objective	Primary Endpoints
To evaluate the ocular safety of a single dose of AG-920 after topical ocular administration of Articaine Sterile Topical Ophthalmic Solution (2 drops 30 seconds apart)	Visual acuity, intraocular pressure, biomicroscopy, AEs, TEAEs, SAEs, withdrawals due to TEAEs
Secondary Objectives	Secondary Endpoints
A subset of up to 20 subjects (with expectations that 12 receiving AG-920 and 6 receiving vehicle) will undergo specular microscopy prior to and 3 months after receiving masked study medication to evaluate the effect of AG-920 on corneal endothelial cell count (ECC).	Mean change from baseline in corneal endothelial cell density after treatment with AG-920

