4 SUBJECT INCLUSION AND EXCLUSION CRITERIA

Subjects must meet all of the following inclusion criteria to be eligible for participation in this study. On criteria that involves the eyes, both eyes must qualify.

4.1 *Subject inclusion criteria*

1. Have provided written informed consent prior to any study-related procedures being performed.
2. Is male or a non-pregnant, non-lactating female aged 18 years or older.
Female subjects of childbearing potential must have a negative urine pregnancy test at Screening (Visit 1) to be eligible for randomization.
3. Are healthy by clinical assessment (detailed medical history), including ocular examination, based on the judgement of the Investigator.
4. [REDACTED]
5. [REDACTED]
6. [REDACTED]
7. [REDACTED]
8. Are willing and able to follow instructions and can be present for the required study visits for the duration of the study.
9. Have verbal communication skills adequate to participate.

Specular microscopy subset subjects only:

10. Have a central corneal endothelial cell density [REDACTED]

4.2 *Subject exclusion criteria*

Subjects who meet any of the following exclusion criteria are ineligible for this study:

1. Have participated in an investigational study (drug or device) within the past 30 days.
2. [REDACTED]
3. [REDACTED]
4. [REDACTED]
5. Have ocular surface disease requiring punctal plugs.
6. Have evidence of any current ocular inflammation.
7. Subject who must wear contact lenses on study visit days.
8. Current ocular allergy symptoms.
9. Any condition, including alcohol or drug dependency, that would limit the subject's ability to comply with the procedures of the protocol (per Investigator's judgment).
10. [REDACTED]

11. The subject or a close relative of the subject is the investigator or a sub-investigator, research assistant, pharmacist, study coordinator, or other staff directly involved in the conduct of the study.

12. [REDACTED]

13. Previous participation in a clinical study of AG-920.

14. [REDACTED]

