6.6 Visit 3 - Specular microscopy (90 days) – subset of subjects ONLY

For subjects in the specular microscopy subset, 90 days \pm 5 days after Visit 2, these subjects will return to the study site for the following assessments:

- Perform of specular microscopy in both eyes.
- Assess for AEs
- Collect any changes to concomitant medications

If there are any ongoing adverse events, the subject will be instructed to return to the investigator's office for appropriate evaluation. If there are no ongoing adverse events, the subject will be considered completed.

Subjects will be thanked for their participation and released to follow their normal standard of care.

6.7 *Unscheduled visits*

To ensure subject safety during the trial, any subject who requires additional follow-up during the study for any reason (that does not fall on a scheduled study visit) should have that visit recorded as an Unscheduled Visit.

6.8 *COVID-19 Pandemic Accommodations*

This study may be conducted during the COVID-19 pandemic. As a result, American Genomics is providing guidance to Investigators on how to modify the current protocol based on [guidance documents from the FDA](#) and other regulatory authorities. The objective of these potential modifications is to ensure the safety of trial participants and clinic staff, maintain compliance with good clinical practice (GCP), and minimize the risks to trial integrity during the COVID-19 pandemic.

To ensure the safety of trial participants and to minimize or eliminate hazards as a result of the COVID-19 pandemic, the following alternative processes and procedures may be implemented when necessary:

1. Depending on local COVID-19 prevalence and prevailing local ordinances and guidances, some screening visit procedures may be conducted by telephone, by video conferencing, or by remote staff in the subject's home.
2. The Randomization/Treatment Visits cannot be done by telephone or video conferencing and must be completed at the investigative site, if it is safe and feasible, per Investigator's judgment.
3. Site specific accommodations should be implemented per state and local guidances possibly including social distancing or personal protective equipment (PPE) requirements.
4. Remote monitoring visits of clinical trial data may be implemented.

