3 STUDY POPULATION

3.1 Definition of Subject Populations

All subjects who have the randomization procedure completed at Day 1 are considered study participants or Randomized Population as defined in the study protocol. The following subject populations are defined to assess the safety of AG-920 in comparison with placebo.

Safety Population

The safety population is defined as all subjects were randomized and who have received at least one drop of the dose (2 drops) of the study medication. The safety population will be utilized as primary population for comparative safety analyses among treatment groups.

Intention-to-treat (ITT) Population

This population is defined as all subjects who are randomized to treatment and have received at least one dose (two drops) of the study medication. Treatment identification is defined in the ITT population by treatment assignment. The ITT population will be identified and finalized before the database is locked and the study is unmasked.

The ITT population is the secondary population for safety evaluation in this study if the ITT population is not identical to the safety population.

Specular Microscopy (SM) Population

The SM population includes those subjects who are randomized and treated and have had the specular microscopy findings for at least one visit.

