5.7 Specular Microscopy

Mean and mean changes in data from the reading center from specular microscopy at baseline and 90 days post dosing from screening will be reported by treatment groups in Table 6.2.1 for the study eye and in Table 6.2.2 for the fellow eye.

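### The secondary objective is the effect of AG-920 on endothelial cells, but the endpoint is a within-arm change and no contrast with vehicle or the fellow eye is pre-specified

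*Protocol*

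**What the plan says.** Protocol Section 2 states the secondary objective as "to evaluate the effect of AG-920 on corneal endothelial cell count (ECC") in a specular microscopy subset of up to 20 subjects, "with expectations that 12 receiving AG-920 and 6 receiving vehicle". The endpoint set against it is "Mean change from baseline in corneal endothelial cell density after treatment with AG-920". Protocol Section 9.4.7, on the analysis of safety, does not mention specular microscopy.

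The SAP describes the analysis in two places. Section 2.9.3 asks for continuous summaries, with means and mean changes by treatment group. Section 5.7 says that these "will be reported by treatment groups in Table 6.2.1 for the study eye and in Table 6.2.2 for the fellow eye". In the SAP's table list (Section 7), Tables 6.2.1 and 6.2.2 are titled as summaries only, whereas the tables for visual acuity, intraocular pressure and biomicroscopy are titled as summary and analysis. For those three measures Section 2.9.3 specifies an ANCOVA of post-dose change between AG-920 and placebo, with the pre-dose value as covariate.

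On the data available:
- One eye is dosed (Protocol Section 5), and all ocular assessments cover both eyes (Protocol Section 6.1).
- Visit 3 calls for this: "Perform of specular microscopy in both eyes" (Protocol Section 6.6).
- Imaging is at Screening and Visit 3 (SAP Section 2.6.3), with values from a central reading center (SAP Section 2.9.3).
- Subset inclusion criterion 10 concerns central cell density. Its limit is redacted. Protocol Section 4 adds: "On criteria that involves the eyes, both eyes must qualify".
- The specular microscopy population takes treated subjects who "have had the specular microscopy findings for at least one visit" (SAP Section 3.1).

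**The concern.** The objective is causal and the endpoint is not. A mean change over 90 days in AG-920 study eyes combines any drug effect with natural cell loss, drift in imaging or reading, and any effect of the vehicle. A small fall could come from any of these, and a mean change near zero could hide a loss offset by drift the other way.

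The tables place the needed columns side by side but do not say which comparison answers the objective or how uncertain it is. This is the only named secondary endpoint, yet it is the eye measure left without a between-arm analysis. A contrast chosen after unmasking would be post hoc.

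**Working it through.** **Inputs.** 12 AG-920 and 6 vehicle subjects (Protocol Section 2; SAP Section 1.1), randomized 2:1 (Protocol Section 3.5). The documents give no SD for the 90-day change and no between-eye correlation of changes, so results are in units of SD, the standard deviation of the 90-day change in one eye. I assume the same SD in both arms and both eyes, and a between-eye correlation rho of 0, 0.5 or 0.7.

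**The plan's own figure.** 18 × 2/3 = 12 and 18 × 1/3 = 6, so the expected split reproduces. No power or precision figure is given for this endpoint.

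**What each quantity estimates.** Let m be natural change plus drift, v the effect of the vehicle drop, S the drug effect in the dosed eye, and F any drug effect in the undosed eye.

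- AG-920 study-eye change (the endpoint as worded): m + v + S
- AG-920 minus vehicle, study eye: (m + v + S) − (m + v) = S
- Study minus fellow eye, AG-920 subjects: (m + v + S) − (m + F) = v + S − F
- The same difference, AG-920 minus vehicle: (v + S − F) − v = S − F

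Only the second isolates S without assuming F = 0. Comparing the fellow-eye difference with vehicle removes v but leaves F, because vehicle subjects have no drug effect in the fellow eye to offset it.

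**95% CI half-widths.**

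- Within AG-920: t(11)/√12 = 2.201/3.464 = 0.64 SD
- AG-920 minus vehicle: t(16) × √(1/12 + 1/6) = 2.120 × 0.5 = 1.06 SD. One covariate leaves 15 degrees of freedom: 2.131 × 0.5 = 1.07 SD, before any gain from adjustment.
- Study minus fellow, AG-920: 0.635 × √(2(1 − rho))
- Its difference from vehicle: 1.06 × √(2(1 − rho))

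| Assumed rho | Study minus fellow, AG-920 | Its difference from vehicle | Plain AG-920 minus vehicle |
|---|---|---|---|
| 0 | 0.90 SD | 1.50 SD | 1.06 SD |
| 0.5 | 0.64 SD | 1.06 SD | 1.06 SD |
| 0.7 | 0.49 SD | 0.82 SD | 1.06 SD |

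Bringing the fellow eye into the between-arm comparison narrows the interval only when rho exceeds 0.5.

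**What 12 against 6 can show.** With a two-sided 5% t test (16 degrees of freedom, noncentrality d/0.5 for a difference of d SD), power for a 1 SD difference is 47%, and 80% power needs 1.49 SD. An observed difference of zero would leave −1.06 to +1.06 SD inside the interval.

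**Subjects with one image.** A change needs both visits, and missing values stay missing (Protocol Section 9.5; SAP Section 2.8), so change summaries already rest on subjects with both images. The separate baseline and Day 90 means need not come from the same subjects.

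**The case against.** The strongest reply is that the plan is controlled. Subjects are randomized and masked, the objective itself counts the vehicle subjects, and the SAP reports mean change by treatment group for both eyes. Natural loss and reader drift act on both arms. Because n, mean and SD are standard summaries (SAP Section 2.9), a reader could compute an unadjusted AG-920-minus-vehicle difference and interval. The subset is small and descriptive, and the study size is set by exposure.

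Most of this stands. A reader of the endpoint alone might infer that the endothelial evaluation is uncontrolled, or that the objective cannot be answered. Neither is supported for the plan as a whole. What remains is that no comparison is declared in advance, and that the descriptive defence fits poorly with the ANCOVA given to the other eye measures. The paired study-minus-fellow interval also cannot be recovered from two separate eye tables, only from subject-level data.

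Two further inferences are tempting:

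- **Regression to the mean from criterion 10.** The limit and its direction are redacted, and no reliability is given. Assume a lower limit between 2 SD below the baseline mean and the mean itself, and reliability R of 0.80 to 0.95. Then (1 − R) × φ(c)/(1 − Φ(c)) gives a spurious fall of 0.003 to 0.16 baseline SD. Dividing by √(2(1 − R)) gives about 0.01 to 0.25 SD of change, below the within-arm half-width of 0.64. It cancels between randomized arms and does not carry the point.
- **The fellow eye as a free gain in precision.** The paired half-widths are smaller than 1.06 SD, but they belong to a different question: drug plus vehicle against no drop.

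**Conclusion.** The point holds as a missing pre-specified contrast, not as missing control data. The protocol endpoint does not estimate the effect named in the objective, and the SAP tabulates the ingredients without combining them.

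The plain between-arm difference in study-eye change should lead, because it alone needs no assumption about the undosed eye. Its half-width of about 1.06 SD assumes that all 12 and 6 subjects supply both images and that the SD is common to the arms. The fellow-eye figures also rest on assumed correlations. Pre-specification would make the answer explicit but not precise: a finding of no difference would not show that the endothelium is unaffected.

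**What to change.** Before unmasking:

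1. Restate the secondary endpoint as the AG-920-minus-vehicle difference in 90-day change in study-eye cell density, adjusted for baseline, with a 95% CI. Add it to SAP Sections 2.9.3 and 5.7.
2. Add as supportive, each with a 95% CI, the study-minus-fellow change within AG-920 subjects and the AG-920-minus-vehicle difference in that quantity. State that both assume no drug effect in the undosed eye, and that the first compares drug plus vehicle with no drop.
3. Show baseline and Day 90 means for subjects with both images.
4. Say that the result is an estimate and that 12 against 6 cannot exclude a sizeable loss.
5. Reconcile the subset size, which is up to 20 in Protocol Section 2 and up to 18 in Protocol Section 3.4.

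The cost is endpoint and SAP wording plus one table beside Tables 6.2.1 and 6.2.2, with no new subjects, visits or images. The drawback is that the intervals will be wide.

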3 STUDY DESIGN

Randomized, placebo-controlled, double-masked, parallel.

3.1 *Description and schedule of visits and procedures*

This is a Phase 3, randomized, placebo-controlled, double-masked, parallel-group design study in healthy subjects performed in the US. It is designed to evaluate the safety of one dose of Articaine Sterile Topical Ophthalmic Solution (AG-920). In this study, subjects who provide informed consent and fulfill all the inclusion criteria and none of the exclusion criteria will be randomized in a 2:1 ratio to receive 2 drops of AG-920 or identical looking placebo into one (study) eye (2 drops 30 seconds apart).

A subset of subjects will undergo endothelial cell count (ECC) evaluations at one site.

A schedule of assessments, including allowable visit windows, is displayed in **Table 1**

3.2 Measures taken to minimize/avoid bias

The Investigator(s), Sponsor, and the subject will be masked to treatment assignment throughout the conduct of the study. Exceptions to this are limited to one statistician at the Contract Research Organization (CRO) who will prepare the randomization code, and three people at the Sponsor who will review the batch records and release product. None of these masked persons will be involved in the day to day execution of the study. The masking will be broken after database lock.

3.3 Study medications

Articaine Sterile Topical Ophthalmic Solution (AG-920) is a sterile, isotonic, non-preserved aqueous solution [REDACTED]

Placebo (vehicle) ophthalmic solution is identical to the active product, with the exception of the active ingredient.

Figure 2: Investigational Medicinal Product

	INVESTIGATIONAL PRODUCT	
PRODUCT NAME	Articaine Sterile Topical Ophthalmic Solution (AG-920)	Placebo (Vehicle)
ACTIVE INGREDIENT	[REDACTED]	[REDACTED]
INACTIVE INGREDIENTS	[REDACTED]	[REDACTED]
UNIT DOSE	0.5 mL blow fill seal vial	0.5 mL blow fill seal vial
ROUTE OF ADMINISTRATION	Topical ocular	Topical ocular
DOSING REGIMEN	2 drops 30 seconds apart from a single vial into study eye	2 drops 30 seconds apart from a single vial into study eye
STORAGE REQUIREMENTS	[REDACTED]	[REDACTED]

3.3.1 IMP Packaging and labeling

Investigational Medical Product (IMP) will be packaged and labeled identically in order to maintain the integrity of the double mask. The appearance of the blow fill seal vials for the AG-920 and matching placebo dosage forms are indistinguishable.

[REDACTED]

The IMP for each individual treatment assignment will be packaged into identical subject kits.

3.3.2 Storage of study medication

The IMP should be stored at room temperature (15-25°C or 59-77°F). Do not freeze the product. Prior to dispensing to the subject, all investigational material must be stored in a secure location with strictly limited access documented by signature of authorized persons who may dispense investigational materials.

3.3.3 Study medication accountability

Accountability of IMP kits will be conducted by a member of the site and verified by a study monitor. Accountability will be ascertained by performing reconciliation between the number of kits sent to the site and the amount used and unused at the time of reconciliation. Site staff will be queried about any discrepancies.

IMP kit shipment records will be verified, and accountability performed by comparing the shipment inventory sheet to the actual quantity of kits received at the site. In addition, receipt of kits will be confirmed by the study monitor. Accurate records of receipt and disposition of the kits (e.g., dates, quantity, subject number, kits used, kits unused, etc.) must be maintained by the Investigator or his/her designee.

At the end of the study and after the monitor has verified kit accountability, all IMP is to be returned to American Genomics (or designee) or destroyed at the site and documented per the site's standard process.

